6.8 Examination of Subgroups

As exploratory analyses, subgroup analyses may be conducted for selected endpoints (see Section 7). Subgroups may include but are not limited to the following:

- ECOG performance status (0–1, 2)
- Cytogenetic risk by MRC (adverse, intermediate/unknown)
- HMA
- Age (<75, ≥75 years old)

- Age (<80, ≥80 years old)
- Gender
- Race
- Geographic region (North America/Australia, Western Europe/Israel, Eastern Europe, Asia)
- Type of AML (de novo AML, secondary AML)
- AML subtype (AML with recurrent genetic abnormalities, AML with myelodysplasia-related changes, AML with therapy-related myeloid neoplasms, AML not otherwise specified)
- Underlying myelodysplasia (yes, no)
- Prior hematological disorder (yes, no)
- Mutational abnormalities (NPM1+, NPM1-)
- Medically unfit for intensive therapy (yes, no)
- Baseline bone marrow blast percentage (20% - 30%, >30%)
- Baseline bone marrow blast percentage (20% - 50%, >50%)
- Baseline WBC (≤5,000, >5,000/μL)
- Baseline WBC (<10,000, ≥10,000/μL)
- Baseline WBC (<15,000, ≥15,000/μL)
- Remission status (CRc, non-responders)
- MRD-negative remission status (MRD-negative CRc, MRD-positive CRc, non-responders)
- Charlson Comorbidity Index (low, moderate, high)
- Hematopoietic Cell Transplantation-Comorbidity Index (HCT-CI; low, intermediate, high)
- Wheatley Risk group (good, standard, poor)
- European ALMA score (favorable, intermediate, unfavorable)
- Treatment-related mortality (TRM) score (low, intermediate, high)

6.9 Covariates

Stratified analyses specified in Section 7.5 will include adjustment for the stratification factors as recorded at randomization. Selected baseline values may be used as covariates in the exploratory analysis of efficacy endpoints.

6.10 Timing of Analyses

Due to safety concerns raised by the IDMC, the study was terminated early prior to the formal interim analyses planned in the protocol. Final analysis will be performed based on 240 patients randomized into the study by the time enrollment was closed.

7 PLANNED ANALYSES

7.1 Disposition

Patient enrollment and disposition will be summarized by treatment group and total using the ITT analysis set. The table will present the number and percentage of patients who were randomized, received study drug, received treatment per randomization assignment, and in follow-up visits. The number and percentage of patients who discontinued treatment will be summarized by the primary reason for treatment discontinuation. The number and percentage of patients who discontinued the study will be summarized by the primary reason for study discontinuation.

The number and percentage of patients randomized in each country and at each site will be summarized by treatment group and total. Disposition data will be listed by patient using the ITT analysis set.

7.2 Demographic and Baseline Characteristics

Demographics and baseline characteristics, including age, gender, ethnicity, race, height, weight, and ECOG score will be listed and summarized; summaries will be presented by treatment group and total using the ITT analysis set.

Disease specific characteristics, including time from initial AML diagnosis, baseline bone marrow blast percentage, baseline WBC, AML subtype, prior hematologic disorder, cytogenetic risk group, mutational abnormalities, Wheatley risk group, European ALMA score, TRM score, Charlson comorbidity index and HCT-CI, will be summarized by treatment group and total using the ITT analysis set. In addition, the number and percentage of patients who receive at least one prior anticancer therapy for hematological disorder will be summarized.

Reasons for enrollment and reasons patients are medically unfit to receive intensive therapy will be summarized by treatment group and total using the ITT analysis set.

The stratification factors entered at the time of randomization and the actual strata at baseline for each patient will be presented in a listing.

7.3 Protocol Deviations

Important protocol deviations (defined as protocol violations by Seattle Genetics) are those that represent a divergence from the protocol that could have a significant effect on the integrity of the study data, or on the subject's rights, safety, or welfare. Important protocol deviations also include exemptions to the study inclusion/exclusion criteria and will be

summarized by category. A list of patients with important protocol deviations will be presented.

7.4 Treatment Administration

Treatment administration will be summarized by treatment group using the safety analysis set. Summary statistics for duration of therapy (weeks), number of cycles per patient, and the number and percentage of patients who were treated at each cycle will be presented. In addition, the cumulative dose, number of doses, average dose per cycle, absolute dose intensity (ADI) and relative dose intensity (RDI) will be described for the blinded study treatment. The number and percentage of patients whose blinded study treatment dose was ever modified will be summarized by modification type (delay, reduction, unplanned dose adjustment), cycle and overall (i.e., overall drug administrations for a patient) for each treatment group. The number and percentage of doses that were modified may also be summarized. Kit errors will be listed.

Duration of therapy is defined as time from the first dose of study drug to the earliest of the following:

- Day 28 of the last treatment cycle
- EOT visit
- Date of death
- Last contact date if the patient is still on treatment at the time of the analysis

Person-time exposure for a treatment group will be calculated by adding the duration of therapy of all patients from the same treatment group.

Intended Dose Intensity (IDI) is defined as the intended dose of drug (e.g., mcg/kg) per unit of time. IDI will be calculated in 2 ways, with and without accounting for the dose modification intended by the investigator.

Absolute Dose Intensity (ADI) is defined as the actual dose (e.g., mcg/kg) per unit of time that the patient received over the entire treatment period. For the purpose of calculating ADI, treatment period is defined as time from the first dose of study drug to Day 28 of the last treatment cycle.

Relative Dose Intensity (RDI) is defined as the absolute dose intensity over the intended dose intensity.

$$RDI = ADI/IDI * 100.$$

Cycle length will be calculated as the interval between Day 1 of 2 consecutive cycles. Cycle length will not be calculated for the last treatment cycle of each patient. The number and percentage of patients with cycle length ≥ 5 weeks will be summarized by cycle and treatment group.

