### **7.7.1.3 Reporting Periods for Adverse Events and Serious Adverse Events**

The safety reporting period for all AEs and SAEs is from study Day 1 (predose) through the EOT visit or 30 days after the last study treatment, whichever is later. However, all study protocol-related AEs are to be recorded from the time of informed consent. All SAEs that occur after the safety reporting period and are considered study treatment-related in the opinion of the investigator should also be reported to the sponsor.

SAEs will be followed until significant changes return to baseline, the event stabilizes (recovering/resolving) or is no longer considered clinically significant by the investigator, or the patient dies or withdraws consent. All non-serious AEs will be followed through the safety reporting period. Certain non-serious AEs of interest may be followed until resolution, return to baseline, or study closure.

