#### **9.3.9.2 Adverse Events**

Adverse events will be defined as treatment emergent if they are newly occurring or worsen following study treatment. The incidence of all AEs, treatment-emergent AEs, and treatment-related AEs will be tabulated. AEs will be classified by system organ class and preferred term using the Medical Dictionary for Regulatory Activities (MedDRA).

AEs will be listed and summarized by treatment arm, MedDRA preferred term, severity, and relationship to study drug. In the event of multiple occurrences of the same AE with the same preferred term in one patient, the AE will be counted once as the occurrence. The incidence of AEs will be tabulated by preferred term and treatment group. AEs leading to premature discontinuation of study drug will be summarized and listed in the same manner.

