6 STATISTICAL CONSIDERATIONS

6.1 General Principles

Descriptive statistics (mean, median, standard deviation, minimum and maximum) will be used to summarize continuous variables. Frequencies and percentages will be used to summarize categorical variables. The median survival time will be estimated using the Kaplan-Meier method; the associated confidence interval (CI) will be calculated based on the complementary log-log transformation (Collett 1994).

Unless otherwise specified, all statistical tests will be performed using a two-sided alpha of 0.05. Confidence intervals will be calculated at a two-sided 95% level. Multiplicity adjustment for alpha level is discussed in Section 6.7.

Any analysis not described in this plan will be considered exploratory, and will be documented in the CSR as a post hoc analysis or a change to the planned analysis.

To comply with regulatory electronic submission guidelines, listings of all clinical data will be submitted as electronic data sets. To facilitate data review for the study report, only pertinent data listings will be created and attached to the appendix of the CSR.

All statistical tables, listings, and figures will be produced using SAS[®], version 9.3 or more recent. Other statistical software, if used, will be described in the CSR.

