7.6.1 Adverse Events

Adverse events (AEs) will be summarized by descending MedDRA preferred term (PT) unless otherwise specified. For incidence reporting, if a patient reports more than one AE that was coded to the same system organ class (SOC) or PT, the patient will be counted only once for that specific SOC or PT.

A treatment-emergent AE is defined as a newly occurring or worsening AE after the first dose of any study treatment. See Appendix C for details regarding treatment-emergent classification. Summaries of AEs will be provided by treatment group and total for the following:

- Pre-existing AEs
- All treatment-emergent AEs

- AEs related to blinded study treatment
- AEs related to azacitidine
- AEs related to decitabine
- Serious Adverse Events (SAEs)
- SAEs related to blinded study treatment
- SAEs related to azacitidine
- SAEs related to decitabine
- AEs leading to blinded study treatment dose delay
- AEs leading to azacitidine dose delay
- AEs leading to decitabine dose delay
- AEs leading to blinded study treatment dose reduction
- AEs leading to azacitidine dose reduction
- AEs leading to decitabine dose reduction
- AEs leading to overall treatment discontinuation
- AEs leading to blinded study treatment discontinuation
- AEs leading to azacitidine discontinuation
- AEs leading to decitabine discontinuation
- Grade 3 or higher treatment-emergent AEs
- Infusion-related reactions (within 24 hours of blinded study drug dose)
- Treatment-emergent AEs by SOC and PT
- Treatment-emergent AEs by SOC, PT, and maximum severity. At each SOC or PT, multiple occurrences of events within a patient are counted only once at the highest severity
- Grade 3 or higher treatment-emergent AEs by SOC and PT
- TEAEs with incidence $\geq 5\%$ by SOC and PT
- SAEs with incidence $\geq 5\%$ by SOC and PT

AEs in the categories below as defined by the Standardized MedDRA Queries (SMQs) or customized searches will be summarized by SOC, PT, and maximum severity. SAEs will be summarized by PT.

- Serious infection
- Bleeding
- Thrombocytopenia
- Neutropenia
- Anemia
- Hepatotoxicity
- Edema
- Pulmonary
- Cardiomyopathy
- Cardiac failure
- Myocardial infarction

All AEs, SAEs, grade 3 or higher treatment-emergent AEs, AEs leading to treatment discontinuation, and AEs with fatal outcome will be listed.

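### SAP 7.4 defines person-time by arm but nothing uses it, so the adverse event tables mix event risk with exposure if time on treatment differs between arms

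*SAP*

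**What the plan says.** - **Person-time.** SAP 7.4 states: "Person-time exposure for a treatment group will be calculated by adding the duration of therapy of all patients from the same treatment group". Its building block is set just before: "Duration of therapy is defined as time from the first dose of study drug to the earliest of the following". The list that follows is Day 28 of the last cycle, the EOT visit, death, and last contact for patients still on treatment. Neither document uses person-time again.
- **AE measure.** SAP 7.6.1 reports incidence by preferred term, by system organ class and preferred term, or by maximum severity. For a patient with repeated events, "the patient will be counted only once for that specific SOC or PT". Protocol 9.3.9.2 agrees: "The incidence of AEs will be tabulated by preferred term and treatment group". No rate per unit of time, time to first AE or cumulative incidence of AEs is planned.
- **AE window.** Protocol 7.7.1.3 sets routine AE reporting "from study Day 1 (predose) through the EOT visit or 30 days after the last study treatment, whichever is later". Treatment itself has no fixed length: it runs to progression, recurrence or unacceptable toxicity (Protocol Synopsis, Duration of Treatment; SAP 4).
- **State of the trial.** SAP 1 says the study was stopped early on safety concerns with 240 patients randomized. SAP 6.7 makes all efficacy analysis descriptive.

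**The concern.** A patient counted once is more likely to be counted the longer he or she is observed. The observation period here depends on response, toxicity and survival, all of which treatment may change. The design assumptions (CRc 20% v 40%, OS hazard ratio 0.70; SAP 6.2) would tend to lengthen treatment in the experimental arm. Toxicity stops and early deaths would shorten it. Crude n/N could therefore show an excess where monthly risk is equal, or hide one where it is not. Safety is the main content left for the abbreviated study report, so the AE tables carry more weight than they would in a completed trial.

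**Working it through.** No stated figure in the plan is at issue, so there is nothing to reproduce. The check has three steps.

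**1. Is person-time used?** No. It appears once, in SAP 7.4. None of the summaries listed in SAP 7.6.1 and none in Protocol 9.3.9.2 takes it as a denominator.

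**2. How large could the effect be?** Monthly risk h and mean exposure m are assumed, because the documents give neither by arm. The hazard is taken as constant and equal in both arms. Two formulas bracket the variation of exposure within an arm:
- every patient has the same exposure: incidence = 1 − exp(−hm)
- exposure is exponentially distributed with mean m: incidence = hm / (1 + hm)

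| h per month | Mean exposure, months | Same exposure | Gap, points | Exponential exposure | Gap, points |
|---|---|---|---|---|---|
| 0.10 | 3 v 5 | 25.9% v 39.3% | 13.4 | 23.1% v 33.3% | 10.3 |
| 0.10 | 2 v 4 | 18.1% v 33.0% | 14.8 | 16.7% v 28.6% | 11.9 |
| 0.05 | 3 v 5 | 13.9% v 22.1% | 8.2 | 13.0% v 20.0% | 7.0 |
| 0.05 | 2 v 4 | 9.5% v 18.1% | 8.6 | 9.1% v 16.7% | 7.6 |

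The true rate ratio is 1.0 in every row. With equal exposure the gap is zero.

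Masking works the same way. Take h = 0.15 with 2.67 months in one arm and h = 0.10 with 4 months in the other. Then hm = 0.15 × 2.67 = 0.40 and 0.10 × 4 = 0.40, so crude incidence is 33.0% in both arms although the rate ratio is 1.5. First-event rates would read 15 v 10 per 100 patient-months.

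**3. Is the 7.4 total the right denominator?** No. Assume 28-day cycles without delay and a last dose on Day 5, 7 or 9 of the cycle. Duration of therapy ends no later than Day 28 of the last cycle; the AE window runs at least to 30 days after the last dose.
- One cycle: 28 days v 5 + 30 = 35 to 9 + 30 = 39 days, which is 25% to 39% longer.
- Four cycles: 112 days v 84 + 35 = 119 to 84 + 39 = 123 days, which is 6% to 10% longer.

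The shortfall is proportionally largest in patients who stop early. The 7.4 total is also not cut at the first event, so it does not give a first-event rate.

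**The case against.** **The AE tables are descriptive and match the protocol.** This stands. No between-arm AE test is planned and no requirement is breached. The point concerns how the tables will be read.

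**Much of the safety question is already time-anchored.** This also stands. SAP 7.5.2.6 gives 30- and 60-day mortality with causes, SAP 7.5.1.2 gives Kaplan-Meier survival, and SAP 7.6.5 splits deaths at 30 days after last treatment. The early-death question is not affected. SAP 7.4 also shows duration of therapy and numbers treated per cycle by arm, so a reader could see an imbalance in exposure. The reader could not correct the AE percentages from those tables.

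**A constant-rate summary has its own bias.** If risk clusters in early cycles, long event-free exposure dilutes a real early excess. This is fair, and it is why the rates should stand beside the crude tables and not replace them.

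**Three stronger readings are tempting but unsupported.**
- A reader might infer that the plan already computes the needed denominator. Step 3 of the working shows that it does not.
- A reader might infer that any rate added later must be labelled post hoc, from "Any analysis not described in this plan will be considered exploratory, and will be documented in the CSR as a post hoc analysis". That sentence goes on to allow for a change to the planned analysis, and SAP 1 permits amendment before database lock.
- A reader might infer that no AE is collected beyond about 30 days after treatment. Protocol 7.7.1.3 keeps later treatment-related SAEs reportable, and Protocol 6.5 and 7.7.1.4 extend SOS/VOD reporting to 180 days after the last blinded dose, with post-transplant follow-up for some patients. The treatment-emergent definition, "A treatment-emergent AE is defined as a newly occurring or worsening AE after the first dose of any study treatment", sets no end date either.

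**Conclusion.** The point holds as a modest improvement. Person-time is defined and never used, and the AE summaries are crude incidences that mix risk with exposure if time on treatment differs between arms. The illustrative size is about 10 to 15 points at 10% monthly risk and about 7 to 9 points at 5%. It rests on assumed hazards, assumed mean exposures of 3 v 5 or 2 v 4 months, and a constant hazard. A reader might infer that the tables will understate, or overstate, toxicity in the experimental arm. The documents do not support either direction, because they give no exposure by arm and the plausible influences on it run both ways. Infusion reactions within 24 hours of a dose are less exposed to the problem, though they still depend on the number of doses received.

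**What to change.** Amend SAP 7.6.1 before database lock. For grade 3 or higher treatment-emergent AEs, SAEs, fatal AEs and the AE categories listed there, add by arm the number of patients with a first event per 100 patient-months, with a 95% CI.

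- **Time at risk:** from first dose to the earliest of first event, death and the end of the AE reporting period ("through the EOT visit or 30 days after the last study treatment, whichever is later"), cut at the data cutoff or last contact.
- **Numerator:** only events that start inside that window. Report later treatment-related SAEs and SOS/VOD separately.
- **Denominator:** not the SAP 7.4 person-time total.
- **Crude tables:** keep them.

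The cost is one derived time-at-risk variable per event category, from dates already collected, and a few extra columns. The downside to state in the report is that a constant-rate summary is approximate when risk clusters in early cycles.

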7.5 Efficacy Analyses

All efficacy analyses will be descriptive in nature and will be presented using the ITT analysis set.

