#### **9.3.5.1 Primary Efficacy Analysis**

**CRc rate** will be analyzed based on the ITT analysis set. The CRc rate between the 2 treatment arms will be compared using a Cochran-Mantel-Haenszel test stratified by the randomization strata. The CRc rate and its 2-sided 99% confidence interval (CI) will be summarized by treatment arm. At the time of the primary analysis of CRc rate, only the first 308 patients randomized will be included in the population for the analysis of CRc rate. CRc rate will also be analyzed for all randomized patients at the time of the final analysis.

**Overall survival** will be assessed using Kaplan-Meier methods. A stratified log-rank test without adjustments for covariates will be used in the primary evaluation of OS differences between the 2 treatment arms based on the ITT population. The hazard ratio will be estimated using the unadjusted stratified Cox model. The 2-sided 95% CI and the CI corresponds to the significance level of the test following the multiplicity adjustment (see Section [9.3.1.5](#)) will be presented. The proportional hazard assumptions will be examined and sensitivity analyses

will be conducted if appropriate. All events entered in the database at the time of the analysis and source-data verified will be included in the analysis of OS, even if there is more than the pre-specified number of events.

Kaplan-Meier curves depicting OS in the 2 treatment arms will be generated. Additionally, the median OS and the probability of OS from 1 month to the end of the follow-up period will be reported at pre-specified intervals. The associated 2-sided 95% CIs will be calculated using the complementary log-log transformation method (Collett 1994). Detailed methodology will be provided in the SAP.

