### 9.3.5.2 Secondary Efficacy Analyses

**MRD-negative CRc rate:** MRD-negative CRc rate will be analyzed based on the ITT analysis set. The MRD-negative CRc rate between the 2 treatment arms will be compared using a Cochran-Mantel-Haenszel test stratified by the randomization strata. The MRD-negative CRc rate and its 2-sided 95% CI will be summarized by treatment arm.

**Duration of remission:** Duration of remission will be analyzed using Kaplan-Meier methodology and Kaplan-Meier plots will be provided by treatment arm using the ITT analysis set. The median remission duration and its 2-sided 95% CI using the complementary log-log transformation method (Collett 1994) will be calculated by treatment arm.

**Event-free survival:** EFS will be analyzed using Kaplan-Meier methodology and Kaplan-Meier plots will be provided by treatment arm using the ITT analysis set. The median EFS and its 2-sided 95% CI using the complementary log-log transformation method (Collett 1994) will be calculated by treatment arm.

**Leukemia-free survival:** LFS will be analyzed using Kaplan-Meier methodology and Kaplan-Meier plots will be provided by treatment arm using the ITT analysis set. The median LFS and its 2-sided 95% CI using the complementary log-log transformation method (Collett 1994) will be calculated by treatment arm.

**Time to complete remission:** TTCR will be summarized by treatment arm using descriptive statistics.

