1 INTRODUCTION

This document outlines the statistical methods to be implemented within the scope of Protocol SGN33A-005, entitled “A randomized, double-blind phase 3 study of vadastuximab talirine (SGN-CD33A) versus placebo in combination with azacitidine or decitabine in the treatment of older patients with newly diagnosed acute myeloid leukemia (AML)”. Results of the proposed analyses will become the basis of the clinical study report (CSR) for this protocol.

The purpose of this plan is to provide specific guidelines from which the analysis will proceed. All planned analyses specified in this document will be performed. Any changes to this plan, in the form of “post hoc” or “data driven” analyses will be identified as such in the final CSR. Any changes will either be reflected in amendments to this plan before the database lock or specifically documented in the CSR.

Due to safety concerns raised by the IDMC, the study was terminated early prior to the formal interim analyses planned in the protocol. Final analysis will be performed based on 240 patients randomized into the study by the time enrollment was closed. This SAP reflects the proposed analyses for the abbreviated CSR.

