2 STUDY OBJECTIVES

2.1 Primary Objective

- To compare the composite complete remission (CRc) rate (morphologic complete remission [CR] and morphologic CR with incomplete hematologic recovery [CRi]) between treatment arms
- To compare overall survival (OS) between treatment arms

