2.2 Secondary Objectives

- To compare the minimal residual disease-negative remission (MRD-negative CRc) rate between treatment arms
- To evaluate the duration of remission in the 2 treatment arms
- To evaluate event-free survival (EFS) in the 2 treatment arms
- To evaluate leukemia-free survival (LFS) in the 2 treatment arms
- To evaluate the safety profiles in the 2 treatment arms
- To evaluate the time to response in the 2 treatment arms
- To evaluate the 30- and 60-day mortality rates in the 2 treatment arms

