6.7 Multiple Comparison/Multiplicity

To maintain strong control of the Type I error rate at 0.05, the fallback procedure proposed by Wiens will be used in the testing of primary endpoints, with an alpha of 0.01 pre-assigned to CRc rate and an alpha of 0.04 pre-assigned to OS (Wiens 2005). If the test for the CRc rate is statistically significant, then the alpha of 0.01 will be re-allocated to OS, and the test for OS will be performed at a 2-sided alpha of 0.05. If the test for the CRc rate is not statistically significant, then the test for OS will be performed at a 2-sided alpha of 0.04.

The parallel gatekeeping principle will be used to control the overall type I error rate of 0.05 (Dmitrienko 2011). The primary endpoints, CRc rate and OS (family 1), will be the gatekeepers for testing the secondary endpoint of MRD-negative CRc rate (family 2). If at least one of the primary endpoints is statistically significant, then a statistical test will be performed for the MRD-negative CRc rate. If both CRc rate and OS are statistically significant, then MRD-negative CRc rate will be tested at an overall alpha of 0.05. If only one of the 2 primary endpoints is statistically significant, then MRD-negative CRc rate will be tested at the corresponding alpha level of the significant primary endpoint. If the tests for both CRc rate and OS are not statistically significant, then the p-value of the test for MRD-negative CRc rate will still be calculated but considered descriptive.

Two formal interim analyses for OS are planned. The test significance level for OS at the interim analysis will be adjusted based on the actual number of OS events observed at each interim analysis according to the O'Brien-Fleming spending function.

Due to safety concerns raised by the IDMC, the study was terminated early prior to the first interim analysis planned in the protocol. Final analysis will be performed based on 240 patients randomized into the study by the time enrollment was closed. All efficacy analysis will be descriptive in nature and no multiple testing procedure will be applied.

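### After early termination the SAP drops the protocol's stratified hazard ratio for OS and specifies no between-arm estimate with a CI, although its objectives still call for comparisons

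*SAP*

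**What the plan says.** **Protocol.** For OS, section 9.3.5.1 plans a stratified log-rank test and an effect estimate: "The hazard ratio will be estimated using the unadjusted stratified Cox model". It asks for a 95% CI, a second CI at the multiplicity-adjusted level, and a check of proportional hazards. For CRc it plans a stratified Cochran-Mantel-Haenszel (CMH) test with a CI for each arm. Section 9.3.5.2 does the same for the main secondary endpoint: "The MRD-negative CRc rate between the 2 treatment arms will be compared using a Cochran-Mantel-Haenszel test stratified by the randomization strata". The protocol names no difference estimator for either response rate and no between-arm analysis of 30- or 60-day mortality.

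**SAP objectives.** Sections 2.1 and 2.2 keep the protocol's comparative wording, for example "To compare overall survival (OS) between treatment arms" and "To compare the minimal residual disease-negative remission (MRD-negative CRc) rate between treatment arms". CRc is worded the same way. For early mortality the verb is to evaluate.

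**SAP analyses.** Section 1 explains the early stop: "Final analysis will be performed based on 240 patients randomized into the study by the time enrollment was closed". Section 6.7 adds "All efficacy analysis will be descriptive in nature and no multiple testing procedure will be applied", and 7.5 opens with "All efficacy analyses will be descriptive in nature and will be presented using the ITT analysis set". Sections 7.5.1.1, 7.5.1.2, 7.5.2.1 and 7.5.2.6 then give, by arm, the CRc rate, Kaplan-Meier curves with medians and landmark survival, the MRD-negative CRc rate, and 30/60-day mortality, with 95% CIs for the estimates. Outside the sample-size text in 6.2, the SAP does not mention a hazard ratio.

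**Text not brought into line.** Section 6.9 still says "Stratified analyses specified in Section 7.5 will include adjustment for the stratification factors as recorded at randomization". Section 9.1, on changes from the protocol, is marked as not applying. Section 9.2.3 does log the removal of efficacy analyses, but as a change from SAP version 3.

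**The concern.** The SAP keeps the objectives of a comparative trial but specifies no output that expresses a comparison. Per-arm intervals are a poor substitute, because judging a difference by whether two intervals overlap is not the same as having an interval for the difference.

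The loss differs by endpoint. For the response and mortality rates, a reader can work out a crude difference from the per-arm counts. For OS, a hazard ratio or a stratified effect cannot be read directly from per-arm curves, medians and landmark rates. OS subgroups by stratification factor remain in 7.5.1.2, but no effect measure is named for them and they do not give one overall stratified estimate.

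The trial was stopped for safety concerns raised by the IDMC. The size and uncertainty of the effect on survival is one of the main things the randomised data can still show.

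**Working it through.** **1. The plan's own figures reproduce.**
- CRc: 20% v 40%, alpha 0.01, 90% power, pooled chi-squared formula without continuity correction. n per arm = [2.576 × √(2 × 0.30 × 0.70) + 1.282 × √(0.16 + 0.24)]² / 0.20² = 153.7, rounded up to 154, so 308 in total as stated.
- OS: HR 0.70, two-sided alpha 0.04, 90% power. Schoenfeld: 4 × (2.054 + 1.282)² / (ln 0.70)² = 350 events. With one O'Brien-Fleming-type efficacy look at 60%, about 353 events are needed, and the stated 354 give 90.2% power.
- At 106 events (the planned first interim), power for HR 0.70 at alpha 0.04 is about 41%. This supports dropping the formal OS test. It does not bear on whether an estimate should be shown.

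**2. What was planned and what remains.**

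| Endpoint | Protocol, between arms | Current SAP, between arms |
|---|---|---|
| OS | Stratified log-rank test; stratified Cox hazard ratio with CI | None |
| CRc | Stratified CMH test | None |
| MRD-negative CRc | Stratified CMH test | None |
| 30/60-day mortality | None | None |

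The hazard ratio is therefore the only named between-arm effect estimate that was removed. For the response rates, what was removed is a test.

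**3. Precision of a hazard ratio.** The documents do not give the final number of deaths. The study ended before the first interim, planned at about 106 deaths, but later deaths may be counted, so 40 to 150 is an assumed range.

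Unstratified, with 1:1 allocation, SE(log HR) = 2/√d, and the 95% CI is the estimate divided and multiplied by exp(1.96 × 2/√d).

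Stratified: four binary factors give 2⁴ = 16 strata, a mean of 240/16 = 15 patients each. The cost was simulated with 300 runs per case, true HR 1, blocks of 4 within strata, uniform follow-up of 1 to 16 months, and exponential survival scaled to d deaths. All of these are assumptions. Cox information I is the sum of p(1−p) over the risk sets at each death, where p is the fraction at risk in one arm. The CI factor is exp(1.96/√I).

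| Deaths d (assumed) | Deaths per stratum | Unstratified factor | I, unstratified | I, stratified | Information lost | Stratified factor |
|---|---|---|---|---|---|---|
| 40 | 2.5 | 1.86 | 9.95 | 9.3 | about 7% | 1.90 |
| 106 | 6.6 | 1.46 | 26.3 | 24.0 | about 9% | 1.49 |
| 150 | 9.4 | 1.38 | 37.1 | 33.1 | about 11% | 1.41 |

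Uneven factor prevalences (assumed 35%, 25%, 50% and 55%) give stratified information of 9.3, 24.1 and 33.3, which is practically the same.

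**4. Precision of rate differences, assuming 120 per arm.**
- CRc at the design rates, 48/120 v 24/120: difference 20 points, Newcombe 95% CI 8.4 to 30.9 (Wald 8.7 to 31.3).
- Mortality, equal in both arms at an assumed p: half-width = 1.96 × √(2p(1−p)/120), which is 5.5 points at 5%, 7.6 at 10% and 10.1 at 20%.

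**5. Internal consistency.** SAP 6.9 points to stratified analyses in 7.5, and 7.5 contains none. SAP 9.1 records no departures from the protocol. Yet the log-rank test, Cox model and CMH tests have gone, and 7.5.2.2 to 7.5.2.5 state that duration of remission, EFS, LFS and time to complete remission will not be analysed.

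**The case against.** The reduction was deliberate and open. The SAP states repeatedly that the trial ended early, calls efficacy descriptive in 6.7 and 7.5, and limits itself in 9.2.3 to what an abbreviated report requires. Protocol 9.3 asks for a protocol amendment only when an analysis change alters site conduct, so that rule was not broken. This stands, and the point is not one of concealment. It does not explain the omission, because the SAP already reports per-arm CIs under the same descriptive label.

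Several narrower points also carry weight:
- Differences for the response and mortality rates would be new, and the mortality objective is to evaluate. They are additions with a weaker claim than the hazard ratio.
- Rewording the objectives would remove the mismatch in wording. It would still leave the OS effect unreported.
- SAP 6.1 and the second sentence of 6.9 leave room for exploratory work, and 7.6.5 reports deaths and their causes by arm. Permission is not specification, and none of these gives an effect estimate.
- The documents do not name the safety concern. If any excess of deaths was early, a single hazard ratio could average over changing hazards, and the landmark rates would be informative. This is a reason to restore the protocol's proportional-hazards check with the hazard ratio.
- The simulation shows the cost in precision only. If the factors are prognostic, stratified and unstratified hazard ratios estimate different quantities, so one must be named as the main estimate.

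**Conclusion.** The point holds. The current SAP specifies no between-arm estimate with a CI for any efficacy endpoint. It omits the one effect estimate the protocol had named, and its objectives still call for comparison. Going descriptive is justified; leaving out the estimate does not follow from it.

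Estimation is feasible with 240 patients. Over the assumed range of 40 to 150 deaths, the hazard ratio's 95% CI factor runs from 1.86 down to 1.38 unstratified and from about 1.90 to 1.41 stratified. The intervals are wide, and showing that is useful. Full stratification costs only about 7% to 11% of the information under the stated assumptions.

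Sections 6.9 and 9.1 are wrong as written, whatever view is taken of the estimates.

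**What to change.** In SAP 7.5, on the ITT set, labelled descriptive and with no claim of significance:
1. Restore the protocol's stratified Cox hazard ratio for OS with a 95% CI as the main estimate, together with the protocol's proportional-hazards check. Note that up to 16 strata may be sparse, and show an unstratified estimate alongside.
2. Add the differences in CRc and MRD-negative CRc rates with 95% CIs, stratified by the randomisation factors.
3. Add the differences in 30- and 60-day mortality with 95% CIs.

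Item 1 is a restoration; items 2 and 3 are additions. Then align 6.9 with the revised 7.5. In 9.1, list the protocol tests, estimates and endpoints that are dropped, with a cross-reference to 9.2.3.

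The cost is SAP wording and a few table rows, with no new data. The Cox model is already in the protocol. The rate differences need an estimator and a CI method to be named.
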